## 9. PARTICIPATING CENTERS

The chosen investigators have documented experience in conducting clinical investigations and in performing colonoscopy procedures, and are able to recruit the desired number of subjects into the study.

---

 Lai E.J. et al, " The Boston Bowel Preparation Scale: A valid and reliable instrument for colonoscopy-oriented research", [Gastrointestinal Endosc. .2009; 69\(3 Pt 2\): 620–625](#)

## 10. STUDY DESIGN

The study is multicenter study ,planned as a single arm, open trial, aimed at evaluating the performance and safety of a colon cleansing device during a colonoscopy procedure in a poorly prepared colons.

Subjects are planned to be enrolled at 3 clinical sites (1 in Germany and 2 in the NL).

Subjects who meet the eligibility criteria will be screened for study participation at a baseline visit(visit 1). Subject who is eligible to the study will required to follow a specific preparation instruction starting 2 days prior to the colonoscopy with the MSC procedure.

Following the procedure a telephone follow-up will be conducted at 48 hours ( $\pm$  24 hours) and 14 days ( $\pm$  3 days) post MCS procedure to assess patient well-being and capture any AEs.

The study design can be seen in the following figure and is detailed in the study procedure section

**Figure 6:** Study design scheme

The detailed study design and scheduled of assessments table can be found in the appendix B.

## **11. SUBJECT POPULATION**

### **11.1. NUMBER OF SUBJECTS**

Up to 47 eligible subjects (up to 15-16 adult eligible subjects per site) that are candidates for diagnostic, screening or surveillance colonoscopy procedure will be enrolled in the study.

Subjects will be considered for the study if they meet the specific inclusion/exclusion criteria.

The criteria for enrollment must be strictly followed.

At least 15% from the entire population will be included in each of the sub groups (i.e., Screening, Surveillance, diagnostic)

### **11.2. INCLUSION CRITERIA**

1. Subjects being considered for diagnostic, screening or surveillance colonoscopy
2. Subjects in the age range of 18-75 years inclusive
3. Subjects with BodyMass Index (BMI) within the range of 18.5-35 inclusive
4. Subject has signed the informed consent

### **11.3. EXCLUSION CRITERIA**

1. Subjects with known Inflammatory Bowel Disease
2. Subjects with known diverticulitis disease or with prior incomplete colonoscopy due to diverticular disease
3. Subjects with known or detected (during colonoscopy) bowel obstruction
4. History of prior surgery to colon and/or rectum
5. ASA $\geq$ IV
6. Renal insufficiency (Creatinine  $\geq$  1.5mg /dL) (based on medical history)
7. Abnormal Liver enzymes (ALT/AST  $\geq$  2 times upper limits of normal) (based on medical history)
8. Subjects taking anticoagulants drugs (excluding aspirin) or dual antiplatelet therapy
9. Subjects with known coagulation disorder (INR  $>$ 1.5).
10. Subjects treated with H2 receptor antagonists or proton pump inhibitors within the 72 hours prior to consuming the Bisacodyl

11. Subjects with active, ongoing lower GI bleeding with hemodynamic instability.
12. Subjects with known Mega Colon
13. Pregnancy (as stated by patient) or breast feeding
14. Subjects with altered mental status/inability to provide informed consent
15. Patients who have participated in another interventional clinical study in the last 2 months

## **12. STUDY PROCEDURES**

### **12.1. SELECTION OF INVESTIGATORS AND TRAINING**

The physicians that will be participate in this trial are experienced colonoscopists.

Each Investigator participating in the clinical trial and the associated clinical study staff will receive training on the clinical protocol. This includes training related to the cleansing evaluation according to the BBPS scoring index, training on AE reporting, case report form (CRF) completion, as well as the device and system (including instruction for use, procedural use, device characteristics, warnings, precautions, and contraindications).

Investigators will be trained in accountability procedures for the investigational products. All experimental devices and materials will be used in accordance with the investigational plan by the clinical staff that have been granted appropriate qualifications and training. Unused devices will be returned to the sponsor.

In addition to the above all study Principal investigators (i.e., [name], [name] and [name]) were trained on the MCS system in an animal model. The training was performed at "Medanex" Clinic , Belgium on July 2015.

### **12.2. SUBJECT ASSIGNMENT**

The study-center will be identified by a single digit number (e.g., 01). The center will assign to enrolled subjects a number in sequence to coincide with the sequence of enrollment. Therefore each subject will be unequivocally identified by a 2-digit center identifier followed by a three digit subject identifier (eg 01-001). Once enrolled at the eligibility assessment visit, the subject will be requested to follow study procedures.

### **12.3. PRE-ENROLLMENT AND ELIGIBILITY ASSESSMENT (VISIT 1)**

Subjects participating in the study may be recruited from investigator's patients pool.

Eligibility assessment shall be conducted prior to the scheduled colonoscopy by phone call and based on the subject's medical history. Candidates who were found to be potentially eligible to participate in the study, will be approached by the investigator to obtain written informed consent prior to any study specific procedures being performed. An explanation on the study purpose, procedures, possible risk and benefits and subject responsibilities to the potential participant will be provided. The subjects will be given the opportunity to evaluate any information about the study in detail and will be allowed to ask the investigator any question regarding the study. The subject's willingness and ability to meet the study requirements will be determined. The investigator must obtain written informed consent prior to subjecting the patient to any study related activity.

### **Visit 1- Screening visit**

Subjects will be assessed for eligibility to participate based on the inclusion and exclusion criteria.

When it has been established that the subject is potentially eligible , written informed consent will be obtained during the visit. The subject will sign and date the consent form. The Investigator will also sign and date the consent form. The original of the informed consent form will be retained with the subject records and a copy will be provided to the subject.

The subject will be recorded on the Subject Enrollment and Visit Log and his/her eligibility will be confirmed.

After eligibility is confirmed, the subject's baseline condition will be assessed and entered to the CRF to include: subject population group, age, gender, race, height, weight, medical records/history and reason for referral.

The colonoscopy procedure will be scheduled to be at least 2 days ahead but no later than 30 days.

In the event that the screening and eligibility assessment takes place more than 30 days prior to the planned procedure date, the investigator should contact the subject prior to the procedure date to assure there is no change in the subject's medical condition.

Subjects will be instructed regarding the preparation regime and will be given the diaries which are needed to be filled out during the preparation phase.

The Physician will instruct the subject to bring the diaries to the scheduled colonoscopy.

Subjects who were found to be not eligible for the study following signature of the Informed Consent Form , will be withdrawn from the study. The following procedures will not be performed in these

subjects, the Subject Enrollment and Visit Log will be completed and the subject eligibility section in visit 1 as well as a "Study Completion" form will be completed in the CRF.

#### **12.4. COLON PREPARATION PROTOCOL**

In a trial to mimic poorly prepped subjects, the subjects will be instructed to follow a limited preparation regimen. An example of proposed bowel preparation regimen is detailed below:

- Split dosing of Bisacodyl\* (2 tablets of 5mg in each dose):
  - First dose: 2 tablets Bisacodyl either in:
    - the early afternoon 1 day prior to colonoscopy (for morning procedures)
    - OR
    - the evening 1 day prior to colonoscopy (for afternoon procedures)
  - Second dose: 2 tablets Bisacodyl either in:
    - the evening 1 day prior to colonoscopy (for morning procedures)
    - OR
    - the early morning on the day of procedure (for afternoon procedures)

The following diet requirements will apply:

- From 2 days prior to colonoscopy until colonoscopy procedure: no dried fruits, seeds, nuts, legumes and a like.
  - Up to 24 hours prior to colonoscopy: clear liquid diet
  - Colonoscopy day: 3 hours before the procedure – no food/liquids
- \* Generic Bisacodyl will be used in the study as routinely used in the participating sites according to the indications of use but following the dosing regime shown above.

The bisacodyl should be use as detailed in the ICF and per the physicians instruction.

- Bisacodyl is taking whole ,by mouth with a full glass of water (8 oz/240 mL), with or without food.
- Drinking extra fluids while taking bisacodyl is recommended.
- Taking Bisacodyl within 1 hour after taking an antacid or milk is not allowed.

An example of the bowel preparation regimen for the subjects can be found in the Appendix C and in the ICF.

## **12.5. COLONOSCOPY PROCEDURE (VISIT 2)**

### Pre-Examination Procedures

- Verify eligibility checked and informed consent was obtained after explaining all risks, benefits, and alternatives to the candidate.
- Verify that the research assistant has collected completed diaries from the subject.
- Verify all background/clinical information, demographic and medical history was documented
  - Note: Subjects that did not take the bowel preparation or failed to complete the bowel preparation will not undergo the procedure and will be excluded from the study.
- Verify all connections and assemblies are properly attached (see Instructions for Use “Setup and Interconnections” section and sections 5.4 and 5.5. in this protocol )
- Verify device works properly (see Instructions for Use “System Operation” section and sections 5.4 and 5.5. in this protocol)
- Place and prepare the subject for the procedure as per standard colonoscopy.
- Perform a digital rectal exam as per standard colonoscopy , evaluate the adequate level of the preparation and start the colonoscopy procedure as per standard of care.

### Colonoscopy procedures

- The procedure will be performed by the clinical investigator(s), experienced in GI endoscopy according to local standard of care. Anesthesia will be applied as well per the standard of care. In order to ensure correct operation of the MCS a Motus GI representative may attend the procedure. Using the MCS, requires specific training with the MCS that will be provided by the sponsor prior to the study. MCS operation is described in the Instruction For Use.
- The MCS will be operated according to section “Operating the MCS workstation” in the IFUs. The colon preparation level for each segment of the colon (Left, Transverse, Right) before the cleansing operation during the insertion phase and post the cleansing operation during withdrawal will be evaluated using the BBPS (Appendix A – Scoring method).
- Once the procedure is completed, relevant data will be recorded on the CRF in addition, findings, diagnosis as well as Physician questionnaire will be recorded/completed.

### **Specific situations occurring during colonoscopy**

- If the attempt to reach the cecum is failed, the investigator shall perform the procedure with a pediatric or any other colonoscope he/she may choose without the MCS. The subject will complete the study as planned.
- If a medical condition requiring treatment is detected during colonoscopy, the subject will be treated as per the standard care.

#### Post-Examination

Subjects will be transferred to recovery room for observation per standard colonoscopy protocol. Subjects will be contacted by phone 48 hours after the procedure to verify that there has been no change in their well-being.

#### Follow-up

Fourteen days after the procedure, each subject will be contacted by phone to verify that there has been no change in their well-being following the procedure. Any AE will be documented in the CRF. Before a subject is considered “lost to follow-up”, there must be at least two documented attempts to contact the subject.

The company may have the option to match the diagnostic and therapeutic interventions performed during the study with the pathologic results from the lab when obtained.

### **12.6. DIARIES:**

Subject diaries are provided to the subject at visit 1 to be filled by the subjects during the preparation phase. This will include diet and bowel movement information. The subject is instructed to bring the diary with him/her to the scheduled colonoscopy.

Additional questions regarding basic demographic information, and health assessment will be filled out in the CRF by the study team.

All subjective assessment questions recorded in the CRF may be used in future studies.

## **13. STUDY COMPLETION PROCEDURES**

### **13.1. SUBJECT COMPLETION OF STUDY**

Subjects are considered to have completed the study if they have completed all study requirements up to the 14 day follow up call. All subjects enrolled in the clinical investigation (including those withdrawn and those who were screened failure) shall be accounted for and documented.

### **13.2. SUBJECT WITHDRAWAL**

Subjects will be withdrawn from the study if one of the following occurs;

- The subject voluntarily discontinues his or her participation in the study.
- Continuation of the course of the study would jeopardize the subject's health and/or welfare (at the discretion of the Investigator)
- There is a concurrent illness (unrelated to treatment) that prevents the subject from complying with the study requirements
- The subject is unwilling or unable to comply with the protocol
- The subject was found to be not-eligible following signature of the Informed Consent Form .

The reasons for the subject's withdrawal from the study must be recorded in the subject's CRF and captured on the Subject Enrollment and Visit Log. All withdrawn subjects having performed the colonoscopy procedure with MCS, will be followed up to 14 days post procedure to verify that there have been no changes in their well-being for the entire period of the study.

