##### **4.2. ANTICIPATED ADVERSE DEVICE EFFECTS**

The potential complications associated with the MCS device are:

- Perforation
- Laceration
- Mild tissue trauma
- Patient infection/biologic reaction

Several steps to mitigate those risks were made (see section 4.3) , following those mitigations the use of the MSC do not increase the risk to the patient.

However as the MCS is used in conjunction with a standard colonoscope during a colonoscopy procedure the complications associated with using the MCS cannot be differentiated from those associated with the colonoscopy procedure.

The risks associated with the colonoscopy procedure along with the procedure itself (i.e., preparation and sedation) as reported in the literature are:

- Colonoscopy-related risk such as bowel perforation, tissue trauma, abdominal pain, bleeding, fever, and infection.
- preparation related risks (lasting >24 hours following colonoscopy) are: Changes in bowel habits, Nausea and vomiting, Dehydration and Renal dysfunction (rare).
- Sedation-related are: cardiovascular disorder, hypotension, and hypoxia
- Death

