#### **4.5. POSSIBLE INTERACTION WITH CONCOMITANT MEDICAL TREATMENT**

The Bowel preparation agent used in this study is generic bisacodyl tablets , and is approved in U.S and in Europe. Bisacodyl belongs to a group of medicines known as stimulant laxatives that increases bowel movements and is considered to be safe with negligible risk of complications.

The anticipated risks associated with this agent are:

- Changes in bowel habits (e.g. Diarrhea, Constipation)
- Nausea & Vomiting
- Dehydration

The preparation in this study is less intensive compared to the standard preparation done prior to colonoscopy procedure, by using only Bisacodyl without the split dose of 4 liter polyethylene glycol (PEG) that is normally required prior to standard colonoscopy procedure.

As the subjects to be enrolled in this study are eligible and referred to standard colonoscopy procedure (I.e., CRC /Surveillance/ diagnostic) we expect that the risks related to the preparation agent will be similar or even lower than the risks following a standard preparation to colonoscopy procedure.

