## 29. APPENDIX B – STUDY DESIGN AND SCHEDULE OF ASSESSMENT

Visit	Visit 1 Screening Visit	Colon Preparation	Visit 2 Colonoscopy ≥ 2 days and ≤ 30 days after visit 1	Follow up 1	Follow up 2
Days	>-2days	-2 to 0 days	0	48 hours ±24 hours	14 day ±3 days
Informed Consent*	X				
Eligibility assessment	X				
Colon Preparation Instructions	X				
Medical History, Concomitant Medications, Demographic details	X				
Diaries	X (providing)	X (by the subjects)			
Bowel Preparation		X (by the subjects)			
Colonoscopy Procedure			X		
Follow Up			X **	X	X
Adverse Events Reporting			X		

\*Informed consent will be obtained prior to the conduct of any study procedures

\*\*Before discharge from the hospital

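### A subject who takes some of the study laxative but is excluded before the procedure has no scheduled safety contact, yet stays in the safety denominator

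*Combined protocol and SAP*

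**What the plan says.** All references are to the combined protocol and SAP.

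- **Enrolment.** Section 12.2 places enrolment at the eligibility visit (Visit 1), before any laxative is taken.
- **Exclusion.** Section 12.5 (Pre-Examination Procedures) says that subjects who did not take the preparation or "failed to complete the bowel preparation will not undergo the procedure and will be excluded from the study".
- **Scheduled calls.** Section 12.5 states "Subjects will be contacted by phone 48 hours after the procedure" and "Fourteen days after the procedure, each subject will be contacted by phone to verify that there has been no change in their well-being". Section 10 gives the same two calls with windows of 24 hours and 3 days either way, also dated from the MCS procedure.
- **Withdrawn subjects.** Section 13.2: "All withdrawn subjects having performed the colonoscopy procedure with MCS, will be followed up to 14 days post procedure". Nothing comparable is stated for subjects withdrawn before the procedure.
- **Safety analysis.** Section 15.2.3 defines the safety set as all enrolled subjects and names the overall AE rate alongside the device-related one.
- **AE recording.** Section 16.3 requires every event that the investigator sees or the subject mentions to be recorded, whatever its cause.
- **Expected harms.** Sections 4.2 and 4.5 list nausea, vomiting and dehydration among the preparation risks, and section 4.2 adds rare renal dysfunction. Section 4.5 states: "we expect that the risks related to the preparation agent will be similar or even lower than the risks following a standard preparation".

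**The concern.** The limited preparation is a deliberate part of this study, and its known harms are the kind that can make someone stop after the first dose. A subject who stops for that reason is removed before the event from which both calls are dated. The overall AE percentage then includes that subject in its denominator without any planned enquiry into what happened.

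The missing information may be related to the outcome, since poor tolerance of the preparation can be the cause of the exclusion. Any resulting bias lowers the overall AE rate. The subjects best placed to contradict the tolerability expectation in section 4.5 are the ones nobody is scheduled to ask. For the subjects themselves, a late-onset problem after a partial dose would come to light only if they reported it.

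**Working it through.** The plan has no figure of its own to reproduce here, so the check is first textual and then illustrative.

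**1. Follow one subject through the text.** The subject enrols at Visit 1 (12.2), takes the first bisacodyl dose, vomits and stops. Section 12.5 excludes the subject and no procedure takes place. The 48-hour and 14-day calls (10, 12.5) have no date to count from. The follow-up promise in 13.2 does not reach this subject. The subject remains in the safety set (15.2.3).

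**2. Ask whether another clause supplies a contact.**

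- Section 16.3 governs what is recorded once an event is known, and schedules no enquiry. Its rule to follow ongoing events to resolution needs a known event.
- Sections 13.2 and 13.3 require a withdrawal reason and an exit form, but state no AE question and no timing for either. A reason saying only that preparation was incomplete would satisfy them.
- The diary is the tool described for the preparation days. Section 12.6 says of it: "This will include diet and bowel movement information". No symptom item is mentioned, although bowel-movement data do bear on one named risk.

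No section schedules a safety contact for this subject.

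**3. Size, simple bound.** Inputs are 47 planned subjects and an allowance of 4 withdrawals for all reasons (15.1). The rate of incomplete preparation is not given, so I assume that *k* of the 4 withdrawn subjects had a preparation AE that was never captured, with *k* from 0 to 4. The rate is the share of subjects with an AE, over all enrolled.

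Understatement = *k*/47:

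| *k* | 0 | 1 | 2 | 3 | 4 |
|---|---|---|---|---|---|
| Percentage points | 0 | 2.1 | 4.3 | 6.4 | 8.5 |

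Worst-case example: 2 subjects with a recorded event give 2/47 = 4.3%. With 4 uncaptured, the true figure is (2 + 4)/47 = 6/47 = 12.8%. The denominator is 47 in both, because 15.2.3 counts all enrolled subjects.

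**4. Size, less extreme assumptions.** Let *m* be the number of unfollowed non-completers, *r* the AE rate in the others and *q* the rate in the non-completers, with none of the non-completers' events captured.

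- True rate = [*r*(47 − *m*) + *qm*]/47
- Observed rate = *r*(47 − *m*)/47
- Share of events missed = 1 − observed/true

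| *m* | *r* | *q* | True | Observed | Missed |
|---|---|---|---|---|---|
| 1 | 5% | 5% | 5.0% | 4.9% | 2% |
| 2 | 5% | 50% | 6.9% | 4.8% | 31% |
| 4 | 10% | 50% | 13.4% | 9.1% | 32% |
| 4 | 5% | 100% | 13.1% | 4.6% | 65% |

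**5. Precision is not the issue.** With zero events, the one-sided 95% upper bound, 1 − 0.05^(1/*n*), is 6.2% for *n* = 47 and 6.7% for *n* = 43. Losing four subjects hardly changes it. The problem is selective ascertainment.

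**The case against.** The strongest reply is that these subjects are not abandoned. Non-completers who attend are identified at Visit 2 by site staff, who collect the diary. Section 13.2 requires the withdrawal reason in the CRF, 13.3 an exit form for everyone who consented, and 13.1 an account of every enrolled subject. Section 16.3 requires any observed or reported event to be recorded and medically managed. A reader might infer from 13.2 that such subjects get no follow-up at all and that preparation harms are systematically lost. The documents do not support that: a visibly dehydrated subject at Visit 2 is an observed AE, to be recorded and, if still ongoing at study end, followed to resolution. The sentence in 13.2 also sets a minimum for one group; it does not forbid following others. What remains exposed is the event that is not raised, starts later, or occurs in someone who does not attend.

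The impact is also limited. The secondary objective concerns safety related to the MCS, and a subject never exposed to the device cannot contribute a device-related event. Subjects who complete the preparation and have the procedure are covered by the visit and both calls. The statement in 4.5 is rationale, not a tested hypothesis.

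Two further inferences should be resisted.

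- **Appendix B.** In the text available, the row "Adverse Events Reporting" has a single mark, under Visit 2, which might suggest that the preparation days are outside AE collection. Read literally it would also exclude the two calls, where sections 10 and 12.5 require AE capture. Merged cells may have been lost, so the row is not evidence either way.
- **Device failure at set-up.** A reader might extend the gap to a fully prepared subject whose device fails. Section 13.2 does not list device failure as a reason for withdrawal, and 15.2.1 removes such cases from the efficacy analysis only. Section 12.5 keeps a subject in the study when the cecum is not reached with the MCS. That extension is not established.

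The narrow point stands: none of these clauses schedules a contact after exclusion for partial preparation.

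**Conclusion.** The plan leaves subjects who took part of the study laxative and were excluded before the procedure without a scheduled safety contact, while counting them in the safety set. Their AEs are liable to under-capture, possibly in a way related to tolerance of the preparation. The size cannot be estimated from the documents. The 0 to 8.5 point range assumes up to four affected subjects; its upper end requires every allowed withdrawal to be a preparation-symptom case with nothing recorded, so it is a bound and not a forecast. Only the overall AE rate and any statement about preparation tolerability are at risk. This is a cheap improvement to data collection and does not undermine the trial's device-safety or performance results.

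**What to change.** Reconcile sections 12.5 and 13.2 and the call schedule with 15.2.3 and 16.3 by three changes:

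1. Give the existing 48-hour and 14-day AE calls to every enrolled subject who took at least one dose of study bisacodyl, counted from the last dose when no procedure takes place.
2. Section 13.2 already requires a withdrawal reason. Where the reason for incomplete preparation is a symptom, also record that symptom as an AE.
3. Tabulate preparation-phase AEs separately, over all subjects who took any dose.

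These change data collection and reporting only; the preparation regimen and the exclusion rule are untouched. Within the plan's withdrawal allowance the cost is at most 4 subjects × 2 calls = 8 calls, plus one table. The reported overall AE rate may rise slightly.
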